10.1. Exposure to BIO 300 Oral Powder

For the SAD study, safety data will also be listed by cohort in order to analyze safety endpoints by dose level. For the MSD study, the number of BIO 300 Oral Powder doses will be calculated and summarized by the mean, standard deviation, median, minimum and maximum values.

10.2. Adverse Events

The FDA guidance entitled "*Toxicity Grading Scale for Healthy Adult and Adolescent Volunteers Enrolled in Preventive Vaccine Clinical Trials*" will be used to grade all AEs. All reported terms and descriptions for AEs will be coded using this FDA guidance and summarized with frequencies and percentages by treatment group, system organ classification (SOC) and preferred term.

All AEs will be included in comprehensive and cohort separated data listings. Additionally, AE summaries will be provided for the following:

- DLT
- Serious AEs (SAEs)
- All Grade 3 or 4 AEs
- AEs leading to discontinuation from the study
- AEs by severity using Toxicity Grading Scale for Healthy Adult and Adolescent Volunteers Enrolled in Preventive Vaccine Clinical Trials grades
- AEs with 10% or higher incidence rates

For all AE summaries, events will be counted only once per subject by primary SOC and preferred term. When an AE occurs more than once for a subject, the maximum severity and causality will be used.

Partial start and end dates for adverse events will be replaced by calendar dates that maximize the duration of the adverse event. The following steps will be followed.

For a partial start date:

1. Replace a missing month with January
2. Replace a missing calendar day with the first of the month

For a partial end date:

1. Replace a missing month with December
2. Replace a missing calendar day with the last day of the month

An end date will not be estimated for adverse events marked continuing at the end of the study.

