8.4.4 TIME PERIOD AND FREQUENCY FOR EVENT ASSESSMENT AND FOLLOW-UP

The occurrence of an adverse event (AE) or serious adverse event (SAE) may come to the attention of study personnel during study visits and interviews of a study participant presenting for medical care, or upon review by a study monitor.

All AEs including local and systemic reactions not meeting the criteria for SAEs will be captured on the appropriate case report form (CRF). Information to be collected includes event description, time of onset, clinician's assessment of severity, relationship to study product (assessed only by those with the

training and authority to make a diagnosis), and time of resolution/stabilization of the event. All AEs occurring while on study must be documented appropriately regardless of relationship. All AEs will be followed to adequate resolution.

Any medical condition that is present at the time that the participant is screened, or after they are screened, but before they are administered the first dose of study drug, will be considered as baseline and not reported as an AE. However, if the study participant's condition deteriorates at any time during the study, it will be recorded as an AE.

Changes in the severity of an AE will be documented to allow an assessment of the duration of the event at each level of severity to be performed. AEs characterized as intermittent require documentation of onset and duration of each episode.

Delegated study personnel will record AEs with start dates occurring any time after the first dose of study intervention is administered through the end of the study. SAEs will be recorded with start dates occurring any time after informed consent is obtained through the end of the study. At each study visit, the investigator will inquire about the occurrence of AE/SAEs since the last visit. Events will be followed for outcome information until resolution or stabilization. Documentation of the serious event will be reported on the Serious Adverse Event CRF and submitted to the Sponsor within 24 hours of awareness.

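### SAP 10.2 completes partial adverse-event dates with no bound at first dose or last study contact, so non-serious events with a missing start day are usually dated before dosing

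*Combined protocol and SAP*

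**What the plan says.** SAP 10.2 states its principle openly: partial AE start and end dates "will be replaced by calendar dates that maximize the duration of the adverse event".

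- Start date: "Replace a missing month with January" and "Replace a missing calendar day with the first of the month".
- End date: "Replace a missing month with December" and "Replace a missing calendar day with the last day of the month".
- The only exception: "An end date will not be estimated for adverse events marked continuing at the end of the study".

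Nothing ties the imputed start to the first dose or the imputed end to the last contact with the subject.

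Protocol 8.4.4 sets the onset window. Staff "will record AEs with start dates occurring any time after the first dose of study intervention is administered". Conditions present before that dose count as baseline and are not AEs. Serious AEs (SAEs) are treated differently: they are recorded from informed consent onward. The same section has changes in severity documented so that the time spent at each severity can be assessed.

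SAP 7.2 says that missing values are left missing in the analyses. It does not mention AE dates.

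**The concern.** For a non-serious AE, the start date must lie between the first dose and the final visit: Day 1 to Day 8 in the SAD cohorts, Day 1 to Day 13 in the multiple-dose cohort. An imputation unit of a month or a year is coarse against windows of 8 and 13 days. With no bounds, the rule can assign an onset that the protocol's own recording rule excludes, and a duration several times the follow-up period.

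At stake are the onset dates and durations in the AE listings, the apparent timing of events relative to dose, and any use of the severity-duration data that Protocol 8.4.4 provides for.

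**Working it through.** The documents give no figure on this point, so there is none to reproduce. The rule is applied literally to the calendar.

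**Inputs from the documents.** The onset window W is 8 days for SAD and 13 days for multiple dose (Protocol 1.1, participant duration). Day 1 is the first dosing day (SAP 7.1). The imputation rules are those of SAP 10.2.

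**Assumptions, not in the documents.** First dose is equally likely on each day of a 365-day year. True onset is equally likely on each day of the window. The year is known. The end-date and duration figures take a 1-day AE.

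**1. Start day missing.** The imputed onset is the 1st of the onset month. It falls before the first dose unless (a) dosing is on the 1st, or (b) onset is in the month after dosing.

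- Dose/onset pairs: 365W
- Pairs under (a): 12W
- Pairs under (b): 12 × W(W − 1)/2
- Share before dosing: [365 − 12 − 6(W − 1)]/365
- SAD: (353 − 42)/365 = 311/365 = 85.2%
- Multiple dose: (353 − 72)/365 = 281/365 = 77.0%

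Direct enumeration of the calendar gives the same two figures. Where the imputed onset is before dosing, it precedes it by 13.6 days (SAD) or 12.5 days (multiple dose) on average, and by 30 days at most.

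Example: first dose 10 February, onset 12 February, day missing. Imputed onset is 1 February, 9 days before dosing. Counter-example: first dose 28 January, onset 2 February. Imputed onset is again 1 February, but this is 4 days after dosing.

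**2. Start month missing.** With the day known, 91.5% of imputed onsets precede dosing in both parts. If first doses are assumed to run from 16 November 2020 to 16 March 2021 (SAD) and from 16 March to 16 July 2021 (multiple dose), this becomes 74% and 100%. With month and day both missing, the imputed date is 1 January and the share is [364 − (W − 1)/2]/365: 360.5/365 = 98.8% (SAD) and 358/365 = 98.1% (multiple dose).

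**3. End dates.** A missing day moves the end later by 14.7 days on average (maximum 30). The result is past the last scheduled visit in 85% (SAD) and 77% (multiple dose). Month and day both missing move it by 182 days on average (maximum 364).

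**4. Duration.** A 1-day AE with both days missing runs from the 1st to the last day of the month, so 28 to 31 days.

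**5. With bounds.** With a floor at first dose, no non-serious AE has a pre-dose imputed onset. If last contact is the last scheduled visit, the 1-day AE in step 4 gets at most 8 days (SAD) or 13 days (multiple dose).

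**The case against.** The strongest reply is that no planned table depends on these dates. The SAP 10.2 summaries count each event once per subject by category, severity or incidence. There is no treatment-emergent date filter, time-to-onset analysis or duration table. Whether something is an AE or baseline is settled when it is recorded. This stands. A reader might infer that the primary safety results are distorted, or that post-dose events would be dropped as pre-existing; the documents do not support either reading.

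A reader might also infer that dose-limiting toxicity counts would shift, because two exceptions in Protocol 7.1 depend on duration. The SAP does not say whether those events are classified from imputed dates, so this cannot be claimed.

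Partial dates should also be rare. Protocol 9.4.4 records dates of occurrence and resolution, Protocol 10.1.8 has missing data queried with the site, and scheduled AE checks are never more than 5 days apart (Day 3 to Day 8; Day 8 to Day 13). A missing month is hard to imagine. This stands too.

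Two further points limit the concern. SAEs can properly start before dosing, so a pre-dose onset is excluded only for non-serious AEs. And Protocol 8.4.4 follows events until their outcome is known, so an end date after the last scheduled visit is not in itself an error.

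The defence that the rule is a deliberate, conservative convention does not stand. For a non-serious AE, the longest duration that the protocol allows begins at first dose. A bounded rule can still maximise duration within that limit.

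**Conclusion.** The concern holds, with low materiality. As written, the rule usually gives a non-serious AE with a missing start day an onset that Protocol 8.4.4 excludes: about 85% of SAD and 77% of multiple-dose cases. It also turns a 1-day event with both days missing into one of 28 to 31 days. The percentages rest on the uniform-calendar assumption and are not document figures.

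It would be too strong to say that the rule fails whenever it is used: 15% (SAD) and 23% (multiple dose) of day-missing onsets are not placed before dosing. A figure near 96% applies only if onset is restricted to the dosing month: 1 − 12/(365 − 42) = 96.3% for SAD and 1 − 12/(365 − 72) = 95.9% for multiple dose.

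The effect is confined to listed onset dates, timing relative to dose and any assessment of duration. AE counts and incidences are unaffected.

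**What to change.** Amend SAP 10.2 and SAP 7.2 before the AE listings are produced:

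- **Non-serious AEs, start:** the later of the earliest date compatible with the recorded part and the first-dose date.
- **SAEs, start:** apply the first-dose floor only when the record shows that the event was post-dose. Otherwise bound the start at the consent date and flag it. Without this exception, a screening SAE in the dosing month with its day missing would be moved to the dosing date and look on-treatment.
- **All AEs, end:** the earlier of the latest compatible date and the last study contact. The last scheduled visit is the wrong bound, because follow-up of an event may continue past it. Keep the existing exception for continuing events.
- **Listings:** flag every imputed date.
- **SAP 7.2:** state that AE dates are an exception to the no-imputation rule.

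The cost is a few lines of SAP text, a small programming change and the separate SAE handling. No new data are needed and no AE count changes. The bounded rule still overstates short events (up to 8 or 13 days for a 1-day AE), which is why the flags are needed.

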10.3. Clinical Laboratory Test Results

Subject minimum and maximum post-baseline laboratory values (and changes from baseline) for analytes measured on a continuous scale will be summarized by the mean, standard deviation, median, minimum and maximum values. The same statistics will be calculated to summarize laboratory test results by visit. Ordinal categorical test results with a corresponding Toxicity Grading Scale for Healthy Adult and Adolescent Volunteers Enrolled in Preventive Vaccine Clinical Trials severity scale will be summarized using shift tables.

Urinalysis tests such as specific gravity and pH were collected only to assess a subjects' eligibility to participate in the study. No analyses are planned for urinalysis test results.

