7.5 DOSE ESCALATION CRITERIA

A Safety Monitoring Committee (SMC) consisting of a Humanetics representative, the Medical Monitor and Principal Investigator, or their recognized delegates will review all available data. The determination for escalation to the next Cohort will require, at a minimum, a review of all safety data of 6 subjects in the previous SAD Cohort through at least Day 3. Decisions to proceed with dose escalations, adding additional subjects to the current Cohort, and possible dose adjustments will be made following this review with the Medical Monitor and Principal Investigator agreeing with the decision. Whether additional information such as PK or PD data may be needed before a decision to escalate can also be determined by the SMC. The primary responsibility of the SMC is to regularly monitor the overall safety of patients enrolled in the study, while protecting the scientific integrity of the study data. Dose escalation criteria will be the following:

- Dose escalation may occur if no more than 2 subjects in a 6-subject cohort experiences a dose-limiting toxicity (DLT, as defined below).
- If 3 DLTs occur (3/6 subjects), an additional 2 subjects will be treated with the same dose.
- If no additional DLTs occur (3/8 subjects), dose escalation may proceed.
- The study sponsor will temporarily cease enrollment for evaluation if in any given cohort 4/8 subjects experience DLTs attributable to BIO 300 Oral Powder as the MTD (maximum tolerated dose) will have been exceeded and no further dose escalation will occur.

DLT is any grade 3 or grade 4 adverse event listed in the draft FDA document entitled "*Toxicity Grading Scale for Healthy Adult and Adolescent Volunteers Enrolled in Preventive Vaccine Clinical Trials*."

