8.4.3 CLASSIFICATION OF AN ADVERSE EVENT

8.4.3.1 SEVERITY OF EVENT

For adverse events (AEs), guidelines based on the FDA Guidance for Industry Toxicity Grading Scale for Healthy Adult and Adolescent Volunteers Enrolled in Preventive Vaccine Clinical Trials will be used to describe severity. The guidance provides a toxicity grading scale (grade 1, mild; grade 2, moderate; grade 3, severe; grade 4, potentially life threatening) for clinical and laboratory abnormalities. For AE

terminology, the NCI Common Terminology Criteria for Adverse Events (CTCAE) version 5.0 will be used, and AE system organ classification will follow the Medical Dictionary for Regulatory Activities (MedDRA).

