9.4.2 ANALYSIS OF THE PRIMARY EFFICACY ENDPOINT(S)

Blood counts, serum chemistry, urinalysis, ECGs, vital signs, and PTT/INR for the study cohorts will be reported as a mean \pm SD at each of the timepoints listed in the **SoA, Section 1.3**. An analysis of covariance (ANCOVA) to compare the cohorts after adjusting for "baseline" (the adjustment covariate) will be completed. Analysis will be performed in individual subjects to identify changes in safety measurements relative to baseline, and between cohorts at the timepoints listed in the **SoA, Section 1.3** to identify any potential dose-response relationships.

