7.1. Definitions

- Baseline is synonymous with screening, and the baseline value (or baseline result) is that measured during the screening visit prior to the first administration of BIO 300 Oral Powder.
- Day 1 is the first day of dosing with BIO 300 Oral Powder.
- Estimand is the estimated value for a parameter or, alternatively, a formula and/or description for how a parameter is estimated.
- Proportional months, defined for durations of time reported in months, are given by the formula

$$\text{months} = \frac{12}{365.25} \times \text{days}$$

- Shift table is a two-way frequency table pairing baseline value with the most extreme post-baseline result.

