9.1. Analysis for Safety Endpoints

Safety data will include adverse events (AEs), safety laboratory (CBC/hematology, serum chemistry and urinalysis), pregnancy (if applicable), drug and alcohol tests test, physical exam, ECG, and vital signs. The proportion of subjects experiencing adverse events, serious adverse events, and DLTs will be summarized for each dosing cohort. See **Section 10** for more information on safety analysis.

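### Read literally, the graded shift tables in SAP 10.3 apply to no analysed laboratory test, so measured values are tabulated by toxicity grade only when reported as adverse events; SAP 9.1 also omits coagulation from its safety laboratory list

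*Combined protocol and SAP*

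**What the plan says.** SAP 10.3 sorts laboratory results by how the test is measured. For each subject's lowest and highest post-baseline value, and for the changes from baseline, results "for analytes measured on a continuous scale will be summarized by the mean, standard deviation, median, minimum and maximum values". The same statistics are given by visit. Shift tables are kept for a second class: "Ordinal categorical test results with a corresponding Toxicity Grading Scale for Healthy Adult and Adolescent Volunteers Enrolled in Preventive Vaccine Clinical Trials severity scale". The section ends with "No analyses are planned for urinalysis test results". SAP 7.1 defines the display: "Shift table is a two-way frequency table pairing baseline value with the most extreme post-baseline result".

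The protocol treats laboratory results as gradable. Protocol 8.4.3.1 describes a scale that runs to "grade 4, potentially life threatening) for clinical and laboratory abnormalities". Protocol 7.5 states the dose-limiting toxicity definition in grades: "DLT is any grade 3 or grade 4 adverse event listed in the draft FDA document entitled". Protocol 7.1 refers to graded AST/ALT and electrolyte abnormalities.

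On the content of the laboratory set, SAP 9.1 lists "safety laboratory (CBC/hematology, serum chemistry and urinalysis" and does not mention coagulation. Protocol 8.1 and 9.1 count coagulation among the safety measures. Protocol 9.4.2 says that blood counts, chemistry, urinalysis, "ECGs, vital signs, and PTT/INR for the study cohorts will be reported" as mean and SD at each scheduled timepoint.

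**The concern.** A phase 1 dose-escalation study should show, at each dose, how many subjects moved from a normal baseline to each grade of laboratory abnormality. SAP 10.3 appears to promise this, but its shift-table class is defined by the type of test, and the blood tests do not belong to that class.

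If the sentence is programmed as written, a value that meets a high grade enters a table by grade only through the adverse event route. Under protocol 9.4.4 that route takes laboratory abnormalities judged clinically significant. The judgment is made in an open-label study in which dose is known. A shift table built from the measured values would not depend on it. This matters for the analytes that protocol 2.2.1 lists as possible risks: amylase, lipase, liver enzymes and red cells.

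The coagulation omission is a smaller matter of the same kind: the SAP's list of safety laboratory tests is narrower than the protocol's.

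**Working it through.** No power or error-rate figure is involved. The check is a count of analytes against the wording of the rule.

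**Step 1. Which blood results are numeric?** Inputs are the Schedule of Activities notes and protocol 8.2.
- CBC: haemoglobin, haematocrit, red cells, white cells, five differential counts and platelets = 10.
- Chemistry and fasting lipids, with total and direct bilirubin counted separately = 24.
- Coagulation: PT/INR and PTT = 2, or 3 if PT and INR are counted separately.
- Total: 10 + 24 + 2 = 36, or 10 + 24 + 3 = 37. Ordinal categorical tests among them: 0.

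**Step 2. Which laboratory results are ordinal?** The urinalysis dipstick determinations (protein, glucose, ketones, blood, bilirubin) = 5. Pregnancy, viral and drug or alcohol tests give a positive or negative result, and SAP 9.1 does not place them in the safety laboratory set.

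**Step 3. Apply SAP 10.3.** The 36 or 37 numeric analytes fall under the descriptive rule. The 5 dipstick items fall in the ordinal class, but no urinalysis analysis is planned. Tests left for the shift-table rule: 5 − 5 = 0.

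**Step 4. Does another section supply the missing step?** SAP 7.1 pairs a baseline value with the most extreme later result. Neither it nor SAP 10.3 says that a numeric value is first converted to a grade. Neither says which direction counts as extreme when an analyte can be abnormal both high and low.

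**Step 5. What reaches a table by grade anyway?** Protocol 8.4.1 allows an abnormal laboratory finding to be an adverse event, and protocol 9.4.4 puts clinically significant ones on the adverse event form. SAP 10.2 grades all adverse events on the same scale, summarises them by treatment group, and gives separate summaries by severity, for Grade 3 or 4 events and for dose-limiting toxicities. SAP 9.1 gives proportions by dosing cohort. Graded laboratory adverse events are therefore tabulated. Graded values not reported as adverse events are not.

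**Step 6. Coagulation samples outside the SAP 9.1 list.** The Schedule of Activities and the blood-volume tables in protocol 8.3.1 and 8.3.2 show draws after the first dose on days 3 and 8 in the single-dose cohorts, and on days 3, 6 and 13 in the multiple-dose cohort. With the minimum numbers completing: 24 × 2 + 8 × 3 = 48 + 24 = 72 samples.

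**The case against.** The strongest reply is that toxicity grades are themselves ordinal categories, so the SAP 10.3 sentence may mean laboratory values once graded. On that reading shift tables are planned and only the wording is loose. This is a fair reading and cannot be excluded. It does not remove the need for an edit. The sentence contrasts its class with analytes measured on a continuous scale, which points to the test itself, and the grading step and the direction are missing on either reading. Two programmers could produce different tables.

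Other points on this side stand and limit the concern:
- A reader might infer that no laboratory toxicity grade is tabulated, or that no grade counts by cohort exist to set beside the dose-limiting toxicity counts. The documents do not support this. SAP 9.1 and 10.2 tabulate graded adverse events by cohort, including laboratory ones, and dose-limiting toxicities are themselves defined as graded adverse events.
- A reader might infer that extreme values disappear into a cohort mean. They do not. The summaries of subject minima and maxima show them, SAP 7 lists all data by cohort, subject and visit, and protocol 9.4.2 plans a review of changes within individual subjects.
- A reader might infer that coagulation goes unanalysed. The SAP 10.3 rule for continuous analytes is unrestricted, SAP 7 computes change from baseline for every measured variable, and protocol 9.4.2 plans mean and SD for PTT/INR. Only the SAP 9.1 list is deficient.
- A reader might take 0 of 36 as the number of graded tables lost. The documents do not reproduce the scale, so the number of gradable analytes is unknown. It could lie anywhere from the few kinds that protocol 7.1 speaks of in grades up to all 36 or 37.

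**Conclusion.** The point holds in a limited form. As written, the SAP 10.3 shift-table rule applies to 0 of the analysed laboratory tests, and no step converts a measured value to a toxicity grade. Tabulation of laboratory results by grade therefore depends on adverse event reporting. SAP 9.1 also omits coagulation, about 72 samples after the first dose at minimum completion, although other provisions would still summarise those results.

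The zero rests on the literal reading of the ordinal class and on urinalysis being the only ordinal test in the safety laboratory set. The missing conversion step does not depend on the literal reading. In a cohort of 6, one subject is 1/6 = 17% of a shift table, so a single shift would be plain to see in one; that figure describes the table and does not measure harm from its absence.

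Nothing in the documents shows that a dose decision depends on this table. Under protocol 7.5 the Safety Monitoring Committee reviews the safety data directly. The gap is in the planned reporting of laboratory toxicity by dose, and it should be closed.

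**What to change.** In SAP 10.3, replace the shift-table sentence with wording to this effect: each numeric haematology, chemistry and coagulation result that has a grade on the named toxicity scale will be converted to that grade; tables of baseline grade against worst post-dose grade will be given by cohort, separately for high and low values where both are graded; results without a grade keep the descriptive summaries. State which analytes are graded, so that the number of tables is fixed in advance.

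In SAP 9.1, add PT/INR and PTT to the safety laboratory list. In the same edit, reconcile urinalysis, which SAP 9.1 and protocol 9.4.2 treat as safety data and SAP 10.3 describes as collected for eligibility only.

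The cost is SAP wording and a small set of standard tables. No new samples, visits or data are needed.
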